The majority of published FR studies to date have been conducted among civilian populations and mainly evaluated the programs' effectiveness at facilitating return to work in low back pain patients with occupational disability.⁴²⁻⁴⁸ Using return to work and/or the number of days of sick leave taken as the main outcome is relevant because the associated costs of disability compensation and productivity losses constitutes a substantial portion of the long-term costs of disability.^{49,50} In a systematic review of FR programs for chronic low back pain, FR programs had a positive impact on the return to work rate in the majority of studies (from 65% to 90%).⁵¹ It should be noted, however, that the variation in the return to work rate is likely associated with the social security system of the country where the program was developed. Another possible reason for the different results in the studies might be that study design, patient population, FR program planning, and other external factors were different and therefore not directly comparable. Other outcomes that have been shown to be positively impacted on the long-term (over approximately 5 years) by the FR program include significantly better functioning on activities of daily living, increased physical activity, and reductions in healthcare utilization and days of sick leave.⁵²

Notably, several prospective outcome studies have been conducted to explore what clinical characteristics of patients predict success in FR programs.⁵³⁻⁵⁵ This is an important factor, since FR programs are expensive and time intensive. The results of these studies indicated that older age, more days of sick leave, no job availability, and higher pain intensity were significantly correlated to poorer outcomes one year after entry into the study. Other studies have also noted that untreated psychosocial factors and secondary gain motivation predict program non-completion as well as poorer outcomes following FR.⁵⁶⁻⁵⁹ Notably, the data from these studies suggest that efforts should be made to propose such programs at an earlier stage of disability, and prior attention to psychosocial factors should be conducted as a work-up towards enrolling patients into an FR program.

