To date, only one study has been published on the effectiveness of the FR program in a military patient population suffering from pain-related disability.⁶⁰ Findings from this study showed positive evidence of FR program outcomes. Participants in the FR program improved significantly compared to the standard treatment group (medication management and injection therapeutics) on self-reported pain, disability, functional status, and fitness for military duty at the post-treatment, 6-month, and 1-year follow-up points. This is the only systematic research study that has been conducted among the military personnel

using standardized functional capacity tests on endurance and lifting strength alongside patient-reported outcomes.⁶¹ **Functional restoration has extensively improved outcomes in the civilian population and prevented long-term disability while promoting a return to optimal function. To date, no studies in the military healthcare settings have identified prognostic factors for successful completion of FR, as well as maintaining satisfactory long-term outcomes. Additionally, there is insufficient published data on the potential benefits of combining FR with a course of integrative pain management modalities.**

9.4

Objectives/Specific Aims/Research Questions:

Describe the purpose and objective(s) of the study, specific aims, and/or research questions/hypotheses

Aim 1: Evaluate the benefit of a program of multimodal pain management therapies prior to an intensive functional restoration program, relative to standard care.

Hypothesis: Patients who complete an IM program prior to FR will demonstrate significantly greater improvements in pain and physical function going into the FR program, relative to standard care. At post-FR, patients who completed an IM program prior to FR will demonstrate significantly improved outcomes on pain severity and physical function at discharge from the program and at 3-months and 6-months post-FR, relative to standard care.

Aim 2: Identify prognostic factors, including demographic factors, psychologic factors, and readiness factors that predict successful outcomes on pain severity and function, as measured by the Defense and Veterans Pain Rating Scale and PROMIS functional status score, respectively, following intensive interdisciplinary functional restoration.

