In addition to IM vs standard care, secondary predictors of outcomes following FR will include: demographic factors (age, military rank, race, household income), psychosocial factors (depression, anxiety, anger); sleep quality and fatigue; medical board status for disability; duration of pain-related disability; prescription opioid dosage; and functional capacity measures of strength and endurance. It is expected that service members with more severe psychological distress and disability at baseline will experience lower rates of positive response following FR.

Aim 3. Evaluate the relationship between legacy paper questionnaires included in the PASTOR-plus packet with PASTOR submeasures.

We will compare legacy paper questionnaires completed by study subjects which include the Tampa Kinesiophobia Questionnaire, Patient Activation Measure, Pain Self-Efficacy Questionnaire, Chronic Pain Acceptance Questionnaire and Roland-Morris Disability Questionnaire, and Pain Catastrophizing Scale with PROMIS measures included in the electronic PASTOR assessment, including pain interference, depression, anxiety, anger, and physical function. This will determine if there are legacy questionnaires with prognostic value which should be added to PASTOR.

Aim 4: Evaluate the relationship between self-reported physical function (from PASTOR) and clinician-supervised tests of physical function, such as exercise treadmill test at all time points.

We will compare self-reported physical function with clinician-supervised tests of physical function to determine if PASTOR respondents over or under-estimate their physical capacity.

Aim 5: Determine whether outcomes differ between the subgroup of participants who completed FR program 4 days per week x 3 weeks vs 2 days per week x 6 weeks

During the course of the study, a protocol modification was approved to allow subjects to participate in the FR program with an extended 2 days per week over 6 week schedule with the same number of treatment hours as the original 4 days per week for 3 weeks. We will evaluate outcomes in both groups to determine if one treatment approach yielded superior outcomes to the other.

Aim 6: Compare outcome measures collected within narrow timelines to those collected within flexible timelines.

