Primary (i.e., primary outcome variables) and secondary endpoints. The primary outcome endpoints are pain intensity and functional status as measured by the PASTOR questionnaire. In addition, secondary predictors of outcomes measures will be evaluated, including demographic factors (age, military rank, household income, race), measures of pain interference, depression, anxiety, anger, sleep quality, fatigue, medical board status for disability, duration of pain-related disability, prescription opioid dosage and functional capacity tests for endurance and strength.

Data analysis.

Aim 1: Evaluate the benefit of a program of multimodal integrative pain management therapies prior to an intensive functional restoration program, relative to standard care.

Hypothesis: Patients who complete an IM program prior to an FR program will demonstrate significantly greater improvements in pain and physical function going into the FR program, relative to standard care. At post-FR, patients who completed an IM program prior to FR will demonstrate significantly improved outcomes on pain severity and physical function at discharge from the program and at 3-months post-FR, relative to standard care.

Analytical Technique: We will use a hierarchical linear model (HLM) for a cluster-randomized trial with time nested within patients.⁷⁷ HLM affords an integrated approach to studying the structure and predictors of individual change, and provides the appropriate standard errors and correct statistical inferences for clustered data. HLM models allow the use of data from patients who are missing one or more observations, where the assumption holds that data are missing at random. Some patients will not follow the intervention protocol, either deliberately by not doing the intervention or due to extenuating circumstances that prevent their participation with the intervention protocol. We will use an intent-to-treat analysis.

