We will initially complete analyses without the inclusion of pre-randomization covariate information. In all analyses, the data will be examined for appropriateness of the statistical assumptions underlying fitted models (e.g., distribution of regression residuals, identification of multivariate outliers representing influential data points, tests for departures from linearity). The primary analysis will examine differences between the control and intervention groups' outcome scores at the 3 month assessment point. To control for inflation of Type I error rates due to co-primary outcomes, alpha will be set to 0.025 for each test of the outcome variables.

If recruitment targets are exceeded to a sufficient magnitude, secondary analyses of change in pain severity and physical function using responder analysis will also be performed. When consensus on minimally important difference (MID) exists, that MID will be used to define response. For PROMIS measures that do not have consensus MID measures, an improvement of one-half of one standard deviation on the PROMIS scale will be considered the minimally important difference for a positive response. Responder analyses require higher sample sizes to detect statistically significant differences but are the preferred method of assessing treatment effect, and permit meaningful comparisons between randomized clinical trials.⁷⁸

Aim 2: Identify prognostic factors that predict successful outcomes on pain severity and function following intensive interdisciplinary functional restoration.

In addition to IM vs standard care, secondary predictors of outcomes following FR will include baseline measures of: demographic variables (age, military rank, race, military occupation), pain characteristics (location, duration, character), psychosocial factors (depression, anxiety, anger); sleep quality and fatigue; medical board status for disability; duration of pain-related disability; prescription opioid dosage; and functional capacity tests for endurance and strength.

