Analytical Technique: The co-primary outcomes for pain severity and physical function will be analyzed using a Sequential Multiple Regression model.⁷⁹ The model will adjust for baseline measures of the co-primary outcomes and pre-FR treatment groups, before assessing the relative importance of secondary outcomes measures (baseline measures of pain interference, depression, anxiety, anger, sleep quality, fatigue, medical board status for disability, duration of pain-related disability, prescription opioid dosage, and functional capacity tests for endurance and strength). Relative importance of predictors among these secondary outcomes will be reported by their respective regression beta weight coefficients. To control for inflation of Type I error rates due to co-primary outcomes, alpha will be set to 0.025 for each test of the outcome variables in their respective regression models.

Aim 3: Evaluate the relationship between legacy paper questionnaires included in the PASTOR-plus packet with PASTOR submeasures.

We will compare legacy paper questionnaires completed by study subjects which include the Tampa Kinesiophobia Questionnaire, Patient Activation Measure, Pain Self-Efficacy Questionnaire, Chronic Pain Acceptance Questionnaire and Roland-Morris Disability Questionnaire, and Pain Catastrophizing Scale with PROMIS measures included in the electronic PASTOR assessment, including pain interference, depression, anxiety, anger, and physical function. This will determine if there are legacy questionnaires with prognostic value which should be added to PASTOR.

Analytical Technique: We will use correlation analysis to determine the relationship between legacy paper questionnaires and PASTOR submeasures.

Aim 4: Evaluate the relationship between self-reported physical function (from PASTOR) and clinician-supervised tests of physical function, such as exercise treadmill test at all timepoints.

We will compare self-reported physical function with clinician-supervised tests of physical function to determine if PASTOR respondents over or under-estimate their physical capacity.

Analytical Technique: We will use correlation analysis to explore the relationship between self-report and clinician supervised tests of physical function.

Aim 5: Determine whether outcomes differ between the subgroup of participants who completed FR program 4 days per week x 3 weeks vs 2 days per week x 6 weeks.

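### Section 11.3 names demographic and pain characteristics as Aim 2 predictors, but the Aim 2 regression it specifies contains none of them

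*Combined protocol and SAP*

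**What the plan says.** Section 9.4 states the objective of Aim 2 as "Identify prognostic factors, including demographic factors, psychologic factors, and readiness factors" that predict pain and function after functional restoration (FR). It then names "demographic factors (age, military rank, race, household income" followed by psychosocial, sleep, disability, opioid and functional capacity measures.

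Section 11.3 gives two further lists. The endpoints paragraph names "demographic factors (age, military rank, household income, race" and then ten clinical items, starting with pain interference. The text under the Aim 2 heading names "demographic variables (age, military rank, race, military occupation), pain characteristics (location, duration, character" and then the psychosocial and other clinical items.

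The Aim 2 analytical technique, also in section 11.3, has two steps. First: "The model will adjust for baseline measures of the co-primary outcomes and pre-FR treatment groups". Then it continues: "before assessing the relative importance of secondary outcomes measures (baseline measures of pain interference, depression, anxiety, anger, sleep quality, fatigue". The rest of the list, running into the sentence on beta weights, reads: "medical board status for disability, duration of pain-related disability, prescription opioid dosage, and functional capacity tests for endurance and strength). Relative importance". Importance is to be reported by regression beta weights, with alpha 0.025 for each co-primary outcome.

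The literature review in section 9.3 reports that "older age, more days of sick leave, no job availability, and higher pain intensity were significantly correlated to poorer outcomes" one year after study entry.

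**The concern.** The technique paragraph is the only model specification for Aim 2. An analyst who follows it fits no demographic term and no pain location, duration or character. An analyst who follows the list directly above it fits a different model. Nothing says which governs, so the choice could be made after the data are seen.

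Two things are at stake. Aim 2 names demographic factors first among the classes it will examine, yet the model as written estimates none of them. Also, beta weights depend on what else is in the model, so a ranking of disability duration, opioid dosage or functional capacity without age and rank may differ from one that includes them. Age is a factor that the protocol's own background reports as related to outcome.

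**Working it through.** **The plan's own figures.** Section 11.2 gives 152 required, 28% loss and 210 enrolled. 152 / (1 − 0.28) = 211.1, or 212 rounded up, against 210 stated; in reverse, 210 × 0.72 = 151.2. This agrees closely enough to use 152 as the number with data. No sample size figure is given for Aim 2.

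**Lists side by side.**

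| Factor | 9.4 | 11.3 endpoints | 11.3 Aim 2 list | 11.3 Aim 2 model |
|---|---|---|---|---|
| Age, rank, race | yes | yes | yes | no |
| Household income | yes | yes | no | no |
| Military occupation | no | no | yes | no |
| Pain location, duration, character | no | no | yes | no |
| Pain interference | no | yes | no | yes |
| Depression, anxiety, anger, sleep, fatigue | yes | yes | yes | yes |
| Board status, disability duration, opioid dosage, functional capacity | yes | yes | yes | yes |
| Readiness | objective only, undefined | no | no | no |

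**Count.** Aim 2 list: 4 demographic + 3 pain + 3 mood + sleep + fatigue + board status + disability duration + opioid dosage + functional tests = 16. The model's second step has 10 items, of which 9 are in that list (the tenth is pain interference). Absent: 16 − 9 = 7, or 7/16 = 44%. This counts the functional tests as one item. Section 10.1 describes five; counting five gives 7/20 = 35%. Disability duration is in the model, but the Aim 2 list names it separately from pain duration.

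**Pattern.** The endpoints list has 4 + 10 = 14 entries. The model's ten items are that list, in the same order, without the four demographic factors.

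**Patients per term (assumed coding).** One term per item, except four or five for the functional tests:

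- As written: 3 (two baselines, group) + 9 + 4 or 5 = 16 or 17 terms; 152/16 = 9.5, 152/17 = 8.9.
- Adding age, rank, race, occupation and pain duration (5): 21 or 22 terms; 152/21 = 7.2, 152/22 = 6.9.
- Adding also income, pain location, pain character and readiness (9 in all): 25 or 26 terms; 152/25 = 6.1, 152/26 = 5.8.
- Fuller categorical coding, 18 to 25 added terms: 34 to 42 terms; 152/34 = 4.5, 152/42 = 3.6.

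**Power for one predictor.** F test with 1 and 152 − p − 1 degrees of freedom, noncentrality 152 × f², partial R² = f²/(1 + f²), alpha 0.025, assumed power 80%. The detectable partial R² is 0.060 with 16 terms (135 df) and still 0.060 with 42 terms (109 df).

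**Shift from leaving age out (illustration).** Shift ≈ standardised age effect × correlation of age with the other predictor, both conditional on the remaining terms. The documents give neither. At 0.1 each: 0.1 × 0.1 = 0.01 SD. At 0.3 each: 0.3 × 0.3 = 0.09 SD.

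**The case against.** The Aim 2 list and the technique paragraph stand under one heading, and the list says the predictors will include the demographic variables. The technique paragraph speaks of secondary outcome measures, a label that does not naturally cover age or race, so it may be incomplete shorthand. That stands to this extent: a reader might infer that demographics were deliberately excluded, and the documents do not show that. They show two texts that disagree. Shorthand does not remove the problem, because this paragraph is the only place where the model terms are set out.

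Other stronger readings are tempting but not supported:

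- **That a readiness variable was dropped.** The term appears in the section 9.4 objective, is undefined, and names no variable in any predictor list. Board status or functional capacity, both in the model, could be what was meant. The only variable the documents call readiness is military medical readiness (sections 10.12 and 14.3), which is not in the model. The supported request is to define the term.
- **That pain interference entered without warrant.** It is missing from two lists, but the endpoints paragraph names it.
- **That predictors would falsely look prognostic.** A variable that tracks age and predicts outcome is prognostic. What adjustment affects is the size and ranking of the beta weights.
- **That the distortion is about 0.09 SD.** That is only the top of an assumed range.

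**Conclusion.** The contradiction holds and rests on the text alone. The Aim 2 model as written has no term for 7 of the 16 predictors in the list directly above it, and none for any demographic factor named in sections 9.4 or 11.3. Its beta weights are therefore unadjusted for age and rank. Baseline pain intensity, another predictor reported in section 9.3, is covered by the first step.

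The effect on the remaining coefficients is not derivable from the documents; 0.01 to 0.09 SD rests wholly on the assumed 0.1 to 0.3 inputs. A reader might infer that the randomised comparison is compromised. It is not: the primary analysis in section 11.3 is the Aim 1 comparison at 3 months, which does not use this model. The point should be corrected before analysis, but it concerns a non-primary aim.

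**What to change.** In the Aim 2 technique paragraph, enter age, rank, race, military occupation and pain duration before the ten listed variables. Most of the data are already planned: age, rank and occupational specialty are on the subject data sheets (section 10.12), demographic data are collected at baseline (Table 8), and pain duration is in the opioid utilization screener (Table 3).

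Then:

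- Add pain location and character if they are collected (Table 8 names neither), or remove them from the Aim 2 list.
- Use one predictor list in section 9.4, section 11.3 and the model, and settle household income against military occupation within it.
- Define readiness factors, for example as the baseline military readiness status that section 10.12 says will be supplied, and enter that variable; or drop the term from Aim 2.
- State category coding and order of entry in advance.

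The cost is SAP wording and fewer patients per term. Coarse grouping keeps the model smaller but discards information about the very factors the aim is meant to examine; finer coding does the reverse. Power for a single predictor barely changes under the assumptions above.

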If the physician determines that the patient is a candidate for the FR program and the patient is willing to commit to this intensive treatment approach, the patient is evaluated by a physical therapist to measure baseline functional status and to determine if he/she has the physical stamina to successfully participate in FR.

The research coordinator or research assistant will perform a brief screen of each potential subject's medical record to determine if he/she has any excluding conditions. If the potential subject has no excluding conditions, the research coordinator or research assistant will meet with him/her to explain the study and to request their consent for study participation. The commanding officer for each subject will be contacted and asked to approve the subject's absence from work as needed for the 6-9 week program.

Randomization

Then, each patient will be randomized to one of two treatment groups: the standard FR program or the FR + integrative modalities (IM) program. Because it is assumed that some participants who randomize to the standard FR program may be interested in IM, the standard FR group will be offered the option of IM following completion of the FR program. The components of the intervention and control treatments are shown in Table 2.

Standard care is comprised of twice weekly health psychology group therapy, twice weekly physical therapy and once-twice weekly occupational therapy during the three weeks prior to FR. Participants on chronic opioid therapy will also be seen by a clinical pharmacist for evaluation for opioid taper. The IM program is comprised of twice weekly acupuncture and chiropractic and once weekly yoga and myofascial release instruction by massage therapist. If indicated, biofeedback and individual massage may also be used. The FR program includes four full days of therapy per week for three weeks. Each FR treatment day will include approximately four-hours of physical activity and one hour each per day of health psychology group therapy and an educational session. Examples of the daily schedules for SC, IM and FR is shown in Figure 2. In an effort to meet enrollment targets, patients who are otherwise eligible for FR program participation but cannot commit to 4 full days of therapy for a three-week period will be given the option of 2 full days of therapy over a six-week period for the same number of contact hours.

Table 2. Intervention and Standard Care

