During the course of the study, a protocol modification was approved to allow subjects to participate in the FR program with an extended 2 days per week over 6 week schedule with the same number of treatment hours as the original 4 days per week for 3 weeks. We will evaluate outcomes in both groups to determine if one treatment approach yielded superior outcomes to the other.

Analytical Technique: We will use a Sequential Multiple Regression model.⁷⁹ We will assess the relative importance of the FR delivery method (either 4 days per week x 3 weeks vs. 2 days per week x 6 weeks controlling for treatment group on our primary outcomes of pain and physical function as well as on the secondary outcomes measures (depression, anxiety, anger, sleep quality, fatigue, medical board status for disability, duration of pain-related disability, prescription opioid dosage, and functional capacity tests for endurance and strength).

Aim 6: Compare outcome measures collected within narrow timelines to those collected within flexible timelines.

We attempted to collect outcome measures at the following timepoints: 1) within one month before starting treatment; 2) within the last day of pre-FR stage through the first day of FR stage; 3) on the last day of FR; 4) 3- and 5) 6- months after the end of FR. However, this precise collection schedule was not always possible. For example, baseline measures were collected more than one month before the start of treatment for study subjects who had conflicts such as military training exercises, personal or family illness or planned leisure travel which postponed the start of study treatment. Collection of follow-up measures was sometimes earlier or later than desired when study subjects with conflicts were unavailable at the time outcomes were requested. We plan to compare outcomes collected within the above timeframes with those collected within timeframes with modest and moderate flexibility as outlined in the following table. This analysis will inform the design of future pragmatic clinical trials in determining acceptable timeline parameters for collection of pain outcomes.

	Baseline	End of pre-FR stage	End of FR stage	Short-term	Intermediate-term
Narrow timelines	w/in 1 month of treatment start	Last day of pre-FR up to start of FR	Last day of FR	3 months after end of FR	6 months after end of FR

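### Aim 5 asks which FR schedule was superior, but schedule was not randomised and the only control named is the randomised IM/SC arm; state baseline adjustment and report a non-randomised association

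*Combined protocol and SAP*

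**What the plan says.** Section 10.1 (Randomization) states that "each patient will be randomized to one of two treatment groups", namely FR preceded by standard care (SC) with or without integrative modalities (IM). FR schedule is no part of that allocation. The same section offers the 2-day, 6-week form to otherwise eligible patients who "cannot commit to 4 full days of therapy for a three-week period". Section 11.3, Aim 5, dates the option: "During the course of the study, a protocol modification was approved to allow subjects to participate in the FR program" on the longer schedule.

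The Aim 5 question is comparative: "We will evaluate outcomes in both groups to determine if one treatment approach yielded superior outcomes to the other". The method is sequential multiple regression, "controlling for treatment group on our primary outcomes of pain and physical function" and on a list of secondary measures. No baseline score, clinical characteristic or period term is named as a control. The aim describes its groups as "the subgroup of participants who completed FR program" on each schedule.

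Aim 2 uses the same type of regression and does name its adjustment: "The model will adjust for baseline measures of the co-primary outcomes and pre-FR treatment groups". The form heading of Section 11.1 asks how confounding will be controlled; the answer refers to Section 11.3, which gives no confounder plan for Aim 5.

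**The concern.** Schedule follows a patient's availability and the date on which FR was taken. Participants who could not free four days a week may differ in baseline pain, function or circumstances from those who could, and all of them took FR after the option opened. A regression on schedule and arm attributes any such difference in outcome to the schedule.

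The one named control does not address this. Arm is randomised before FR, so it should be roughly independent of schedule, and conditioning on it changes the schedule contrast little.

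At stake is the Aim 5 conclusion alone. Followed as written, the analysis could report one schedule as better when the groups differed before FR began, and a programme might choose its delivery format on that basis.

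**Working it through.** Aim 5 states no sample size, alpha or effect, so there is no planned figure to reproduce. The calculation shows how the model behaves if the true schedule effect is zero.

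**Inputs from the documents.** N = 152 (Section 11.2, the overall required sample, not an Aim 5 count). Two-sided alpha 0.025 (Section 11.3, Aims 1 and 2; Aim 5 gives none), so z = 2.241.

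**Assumed inputs.** Baseline-outcome correlation r = 0.5; n6 = 15 or 38 on the 6-week form; baseline gap g = 0.2, 0.3 or 0.5 SD between schedules.

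**Formula.** With spurious difference d in SD units and se = √(1/n6 + 1/(152 − n6)), the false-positive rate is Φ(−z + d/se) + Φ(−z − d/se). For n6 = 15, se = 0.272; for n6 = 38, se = 0.187.

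**Case A: the gap acts only through the measured baseline score.** Here d = r × g = 0.10, 0.15, 0.25 SD. Worked example, n6 = 38 and g = 0.5: d/se = 0.25/0.1873 = 1.335, and Φ(−0.907) + Φ(−3.576) gives 18.2%. Once the baseline score is in the model, the expected bias is zero.

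**Case B: the gap is a stable group difference, present at baseline and follow-up alike.** Here d = g as written. Adjustment leaves g × (1 − r) = 0.10, 0.15, 0.25 SD, against a residual SD of √(1 − r²) = 0.866.

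False-positive rates (%) for g = 0.2 / 0.3 / 0.5. As-written figures use the formula; adjusted figures come from simulation with 4000 replicates.

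| Case | n6 | As written (schedule + arm) | Plus baseline score |
|---|---|---|---|
| A | 15 | 3.5 / 4.8 / 9.4 | 2.6 / 2.5 / 2.4 |
| A | 38 | 4.7 / 7.6 / 18.2 | 2.4 / 2.6 / 2.7 |
| B | 15 | 6.7 / 12.8 / 34.4 | 3.9 / 5.3 / 11.5 |
| B | 38 | 12.1 / 26.1 / 66.6 | 5.9 / 8.9 / 22.9 |

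Simulating the as-written model in case B gives 6.5 to 33.8% (n6 = 15) and 11.8 to 65.8% (n6 = 38), in line with the formula.

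**Calendar period.** Suppose outcomes shift by 0.2 SD between periods and 76 of 152 start FR after the change. Everyone on the 6-week form is in the later period, against (76 − n6)/(152 − n6) of the 3-week group. The bias is 0.2 × 76/(152 − n6): 0.11 SD for n6 = 15 and 0.13 SD for n6 = 38. With no baseline gap, simulated rejection is 3.6% and 7.2% with the baseline score in the model, and 2.5% and 2.8% once a period term is added. Baseline adjustment does not deal with a period shift.

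**Precision cost of the period term.** The schedule contrast then rests on later starters. The standard-error ratio is √(1/n6 + 1/(n_after − n6)) / √(1/n6 + 1/(152 − n6)).

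| Starting FR after the change | n6 = 15 | n6 = 38 |
|---|---|---|
| 46 | 1.16 | 2.08 |
| 76 | 1.06 | 1.22 |
| 106 | 1.02 | 1.08 |

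The 2.08 arises because only 46 − 38 = 8 later starters remain on the 3-week form.

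**The case against.** The best reply is that Aim 5 is an abbreviated Aim 2. It uses the same named regression with the same reference. Sequential regression enters predictors in blocks, and Aim 2 states its first block. Aim 5's list of secondary measures is close to Aim 2's and includes items, such as duration of disability, that make little sense as outcomes of a schedule. The baseline block may have been meant to carry over. This stands as a drafting ambiguity, but the text does not say so, and calendar period would still be uncontrolled. The Aim 1 sentence "We will initially complete analyses without the inclusion of pre-randomization covariate information" does not settle it either: it sits under another aim and names no covariates.

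A second reply is that availability is not severity, so the gap may be near zero. That is fair. The stated reason for the 2-day form is time commitment, and the documents describe no trend in pain or function over calendar time. Aim 6 does list illness and training among the conflicts that delayed treatment. It is plausible, but not shown, that similar conflicts influence schedule choice.

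Third, a reader might infer that Aim 5 drops everyone who stopped early. The word *completed* allows that reading, but the same aim also speaks simply of both groups, and Section 13.7 describes disenrolment by the clinical team as rare. The completer reading is possible, not established.

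Finally, Aim 5 is not the primary analysis. That limits the consequence without supplying the missing control.

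**Conclusion.** The concern holds in a limited form. Aim 5 poses a superiority question about a non-randomised factor, and the one control it names does little against selection into a schedule. That rests on the text alone.

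The size does not. Gap, correlation, number on the 6-week form, period shift and share starting after the change are all assumed. On those assumptions the as-written false-positive rate against a nominal 2.5% is about 3.5 to 18% in case A and about 6.5 to 66% in case B.

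Two stronger readings are not supported. One is that the schedule groups did differ: the documents report no such difference. The other is that adding the baseline score cures the problem: it restores about 2.5% only in case A, and leaves about 4 to 23% in case B. Adjustment reduces the bias without guaranteeing its removal, so the wording of the conclusion must change as well. The randomised IM versus SC comparison in Aim 1 is untouched.

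**What to change.** In Section 11.3, Aim 5:

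1. Adjust each model for the baseline value of its outcome, at minimum baseline pain and physical function as in Aim 2, and keep treatment group. If Aim 2's block was intended, say so.
2. Replace the superiority wording with an adjusted, non-randomised association, and state that unmeasured selection may remain.
3. As a sensitivity analysis, add a term for FR start before or after the 2-day option opened, or restrict to later starters. Use the FR start date, since FR begins at least three weeks into treatment and some starts were postponed. Report the loss of precision.
4. Group participants by the schedule they started.

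The cost is SAP wording. Baseline scores are collected under Section 10.1 and FR start dates under Section 10.12. Item 1 adds one or two terms per model. Item 3 has a real price, from a 2% to a 108% larger standard error in the cases tabulated, which is why it belongs in a sensitivity analysis.
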